7.1.8. Exposure-adjusted TEAE Rate

The exposure-adjusted TEAE rate is defined as the number of subjects with a specific event divided by the total exposure-time among the subjects in the treatment group and at risk of an initial occurrence of the event. Specifically,

Exposure-Adjusted TEAE Rate $= \frac{n}{T} = \frac{n}{\sum t_i}$

Where *n* is the number of subjects with events, t_i is the i^{th} subject exposure time in years and *T* is the total exposure time in years of all subjects. If a subject has multiple events, the t_i is the time of the first event. For a subject with no event, the t_i will be censored at the time of data cut-off date if the subject is still taking IDELA; and the t_i will be censored at the time of last does date plus 30 days or data cutoff date whichever is earlier if the subject discontinues IDELA.

The exposure-adjusted TEAE rate will be summarized for AEI by treatment group based on the FAS.

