7.1.5. Treatment-Emergent Adverse Events

7.1.5.1. Definition of Treatment-Emergent

TEAEs are events in a given study period that meet one of the following criteria:

- Events with onset dates on or after the start of IDELA and up to 30 days after the permanent discontinuation of IDELA.
- AEs resulting in IDELA discontinuation after the start of treatment.

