7.1.7. Treatment-Emergent Adverse Events of Interest

The treatment-emergent AEs of interest (AEI) include:

- **Rash** based on Gilead medical search list including multiple MedDRA preferred terms dermatitis exfoliative, drug eruption, rash, rash erythematous, rash generalised, rash macular, rash maculo-papular, rash papular, rash prutitic, rash morbilliform, and exfoliative rash
- Diarrhea/Colitis including diarrhea or colitis

• Pneumonitis

- Anaphylaxis including anaphylactic reaction, anaphylactic shock, anaphylactic transfusion reaction, anaphylactoid reaction, anaphylactoid shock, circulatory collapse, first use syndrome, kounis syndrome, shock, type I hypersensitivity
- **Bowel perforation** including rectal perforation, duodenal perforation, duodenal ulcer perforation, duodenal ulcer perforation obstructive, diverticular perforation, gastrointestinal perforation, gastrointestinal ulcer perforation, appendicitis perforated, ileal perforation, ileal ulcer perforation, intestinal perforation, intestinal ulcer perforation, jejunal perforation, jejunal perforation, large intestinal ulcer perforation, large intestinal ulcer perforation, small intestinal perforation, small intestinal ulcer perforation

Summaries of TEAEs of interest will be provided for the following:

- AEIs by CTCAE Grade
- AEIs leading to modification (interruption and/or reduction)
- AEIs leading to interruption
- AEIs leading to reduction
- AEIs leading to IDELA discontinuation
- AEIs by time interval (12 weeks intervals)

Incidence and prevalence of AEIs by time interval will be summarized by 12 weeks intervals up to 84 weeks (eg, 0 to < 12 weeks, 12 to < 24 weeks, ..., 72 to < 84 weeks) and \ge 84 weeks. Incidence of AEIs in the interval is defined as the proportion of subjects with onset of AEI in that interval out of those at risk at the beginning of the interval. Prevalence of AEI is defined as the proportion of subjects experiencing AEI in that interval out of those at risk at the beginning of the interval. The subjects at risk include those on IDELA or within 30 days post last dose date for subjects who didn't die at the beginning of the interval.

• Time to first onset and resolution of AEIs

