Time to onset of AEIs (in weeks) is defined as time from the baseline reference date for safety endpoints to the date of first incident of AEI. In the absence of an event, the onset date will be censored at the earliest from the following dates: last IDELA dosing date (ie, captured on study drug completion CRF page) + 30 days, analysis data cut-off date and death date. Time to resolution of AEIs is calculated as (AEI stop date – start date of first occurrence of AEI + 1) / 7.

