7.2.3.3. Exposure-adjusted Treatment-Emergent Laboratory Abnormalities Rate

The exposure-adjusted treatment-emergent lab abnormalities will be analyzed similarly to the exposure-adjusted TEAE rates (outlined in Section 7.1.8).

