7.2.5. Transaminase Elevations

Analyses of transaminase elevations will be based on laboratory values using the FAS. Number and percentage of subjects will be summarized by treatment groups for subjects:

- with Grade 3 or 4 alanine aminotransferase (ALT)/aspartate aminotransferase (AST) elevation
- with Grade 3 or 4 ALT/AST elevation resolved to both ALT/AST of Grade 1 or less
- re-challenged after dose interruption
- with recurrence of Grade 3 or 4 ALT/AST elevation among re-challenged
- with recurrent Grade 3 or 4 ALT/AST elevation resolved to both ALT/AST of Grade 1 or less

Kaplan-Meier curves and estimates will be provided for time to onset of first Grade 3 or 4 treatment-emergent ALT/AST elevations. Time to onset of first event is defined as time from the baseline reference date for safety endpoints to the start date of first Grade 3 or 4 treatment-emergent ALT/AST elevation, ie, time in weeks is calculated as (start date of first occurrence – baseline reference date for safety endpoints + 1) / 7. In the absence of an event, the censoring date applied will be the earliest from the following dates: last dose date (if treatment discontinued) + 30 days, analysis data cut-off date and death date.

For subjects with at least 1 episode of Grade 3 or 4 ALT/AST elevation, time to resolution of the first episode of treatment-emergent Grade 3 or 4 ALT/AST elevation to Grade 1 or less will be summarized using Kaplan-Meier estimates. The same censoring rule described above for time to onset will be used.

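### SAP 7.1.8 does not stop time at risk at death, so some exposure-adjusted event rates would be slightly understated

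*SAP*

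**What the plan says.** SAP 7.1.8 defines the rate as the number of subjects with the event divided by the "total exposure-time among the subjects in the treatment group and at risk of an initial occurrence of the event". A subject with the event contributes time up to the first occurrence. For a subject without it, there are two cases. The time "will be censored at the time of data cut-off date if the subject is still taking IDELA"; after discontinuation it "will be censored at the time of last does date plus 30 days or data cutoff date whichever is earlier". Neither clause mentions death.

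SAP 7.2.3.3 states that laboratory abnormality rates "will be analyzed similarly to the exposure-adjusted TEAE rates".

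Three related rules in the same SAP do account for death:

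- Time to onset of adverse events of interest (7.1.7) is censored at the earliest of "last IDELA dosing date (ie, captured on study drug completion CRF page) + 30 days, analysis data cut-off date and death date".
- Time to first Grade 3 or 4 ALT/AST elevation (7.2.5) is censored at the earliest of "last dose date (if treatment discontinued) + 30 days, analysis data cut-off date and death date".
- The risk set for the 12-week incidence and prevalence tables (7.1.7) consists of subjects on idelalisib or "within 30 days post last dose date for subjects who didn't die at the beginning of the interval".

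Nothing elsewhere in the SAP ends the time in 7.1.8 at death.

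**The concern.** A subject who has died cannot have a first event, so days after death do not belong in a denominator that 7.1.8 itself describes as time at risk. Followed literally, the clause keeps such a subject in the denominator until 30 days after the last dose or until the cutoff.

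The numerator is unaffected and the denominator can only grow, so any error is downward. For a safety rate, that is the unfavourable direction. The error also need not be equal across the treatment groups whose rates will be read side by side.

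There is a practical consequence for programming as well. For the same adverse events of interest, Table 3.1.24.8 (time to first onset) would use time that stops at death, and Table 3.1.24.9 (exposure-adjusted rate) would use time that does not.

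**Working it through.** The plan states no exposure-adjusted rate, so there is no figure to reproduce. The check compares the rule as written with the same rule plus a death term.

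**Who is affected.** A subject adds excess time for a given event only if all three conditions hold:

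1. The subject has not had that event. Otherwise time stops at the first event.
2. Death comes before last dose + 30 days.
3. Death comes before the data cutoff.

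**Excess per subject.** Excess = min(last dose + 30 days, cutoff) − death date. It is largest when death falls on the last dosing day: 30 / 365.25 = 0.082 year. This cap takes a subject who dies on treatment to be classed as discontinued.

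**Effect on the rate.** Let n be the number of subjects with the event, T the correct person-time and E the total excess. The rate as written is n / (T + E), and with death in the minimum it is n / T. Let Tbar be the correct mean time at risk in years, d the share of the group dying event-free inside the window, and g the days from last dose to death. If the cutoff does not intervene:

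Relative shortfall = 1 − Tbar / (Tbar + d × (30 − g) / 365.25)

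The group size cancels.

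**Inputs.** The 30 days come from SAP 7.1.8. The values of d, Tbar and g are not in the documents. I assumed d from 5% to 30%, Tbar from 0.25 to 2 years, and g of 0 or 10 days.

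| Tbar (years) | d = 5%, g = 0 | d = 30%, g = 0 | d = 5%, g = 10 | d = 30%, g = 10 |
|---|---|---|---|---|
| 0.25 | 1.62% | 8.97% | 1.08% | 6.17% |
| 0.5 | 0.81% | 4.70% | 0.54% | 3.18% |
| 1 | 0.41% | 2.40% | 0.27% | 1.62% |
| 2 | 0.20% | 1.22% | 0.14% | 0.81% |

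One cell in full: for Tbar = 1, d = 30%, g = 0, the excess is 0.30 × 30 / 365.25 = 0.0246 year per subject, and 1 − 1 / 1.0246 = 2.4%.

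**The same in rates.** Take an assumed group of 100 subjects, 20 with the event and 100 correct person-years, so the correct rate is 20.00 per 100 person-years.

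| Event-free deaths in window | Excess person-years (g = 0) | Rate as written (g = 0) | Rate as written (g = 10) |
|---|---|---|---|
| 5 | 0.41 | 19.92 | 19.95 |
| 10 | 0.82 | 19.84 | 19.89 |
| 20 | 1.64 | 19.68 | 19.78 |

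**The case against.** The best defence is that the window in 7.1.8 mirrors the SAP's treatment-emergent definition, which takes in events "up to 30 days after the permanent discontinuation of IDELA" and has no death term either. That does not rescue the clause. The treatment-emergent window decides which events count, and no event can start after death, so it needs no death term. A denominator does. Nor is 7.1.8 simply a measure of dosing duration: SAP 4.3.1 defines exposure duration without the extra 30 days.

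Other parts of the defence stand:

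- The effect is small on plausible inputs, and SAP 3.5.2 plans only descriptive analyses. No test, threshold or stopping rule uses these rates.
- The wording of 7.2.3.3 requires only similar analysis, so carrying the exact clause over to laboratory rates is the natural reading but still an inference.
- The calculation counts every assumed early death as event-free. That suits rare events. For common events or laboratory abnormalities, many subjects who die will already have had the event and add nothing.

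A reader might infer more than the text supports:

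- **That every exposure-adjusted rate is too low.** A combination of event and group with no event-free death inside the window is exact, and a death more than 30 days after the last dose adds no excess.
- **That the group with the most on-treatment deaths is distorted most.** The relative error follows event-free early deaths per unit of person-time, so a group with more deaths but longer follow-up can be affected less.
- **That all these rates conflict with a time-to-onset analysis.** Death-censored onset rules exist only for adverse events of interest and for Grade 3 or 4 ALT/AST elevation.

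**Conclusion.** The point holds as a minor error in a stated rule. As written, 7.1.8 counts up to 30 days of person-time after death for event-free subjects who die before both last dose + 30 days and the cutoff. This conflicts with its own description of the denominator and with 7.1.7 and 7.2.5. The direction is certain: wherever such a subject exists, the rate is understated.

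The size is not known from the documents. At about one year of mean time at risk it is roughly 0.4% to 2.4%, if 5% to 30% of the group die event-free on the last dosing day. It falls by about a third if death comes 10 days later. Errors of 5% or more appear only at the extreme of the assumed range, with a mean of about three months at risk and many event-free deaths close to the last dose. No conclusion of the study is likely to turn on it.

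**What to change.** In SAP 7.1.8, replace the two clauses for event-free subjects with one rule: time ends at the earliest of last dose + 30 days (if idelalisib was discontinued), the data cutoff date and the death date. This matches 7.1.7 and 7.2.5. It also covers a subject who dies while still recorded as taking idelalisib, whose time would otherwise run to the cutoff on a literal reading. In 7.2.3.3, state that laboratory rates use the same rule.

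The tables affected are 3.1.23, 3.1.24.9, 3.2.4 and 3.3.4. The cost is one sentence in each section and one more argument in the programmed minimum. No new data are needed, since the time-to-onset rules and the overall survival analysis already require death dates.

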7.2. Laboratory Evaluations

Summaries of laboratory data (including hematology, serum chemistry, urinalysis, and selected immunoglobulin parameters) will be provided. Summaries of laboratory data will be based on observed data and will be reported using SI units. The focus of laboratory data summarization will be on treatment-emergent laboratory abnormalities using the FAS.

7.2.1. Summaries of Numeric Laboratory Results

Descriptive statistics (sample size, mean, StD, median, Q1, Q3, minimum and maximum) will be provided for each laboratory test specified in the study protocol as follows:

- Baseline values
- Values at each post-baseline visit
- Change from baseline at each post-baseline visit

In the case of multiple values in an analysis window, data will be selected for analysis as described in Section 3.6.2. In addition, mean change from baseline (\pm standard error) and median (\pm Q1/Q3) for selected lab parameters will be plotted over time by treatment groups.

7.2.2. Summaries of Categorical Laboratory Results

Laboratory data that are categorical will be summarized using number and percentage of subjects in the study with the given response by treatment groups and visit based on analysis window.

7.2.3. Graded Laboratory Values

Applicable hematological and serum biochemistry laboratory data will be programmatically graded according to CTCAE, Version 4.03 severity grade [grade laboratory results as Grade 0, mild (Grade 1), moderate (Grade 2), severe (Grade 3), or life threatening (Grade 4)]. Grade 0 includes all values that do not meet criteria for an abnormality of at least Grade 1. Some laboratory tests have criteria for both increased and decreased levels; analyses for each direction (ie, increased, decreased) will be presented separately. For all laboratory tests except for lipids (cholesterol and triglyceride), lab normal ranges will override the common terminology criteria (CTC) grade criteria (ie, all labs within normal ranges will be programmatically assigned a CTCAE grade of 0) when lab normal ranges overlaps with CTC grade criteria. Local labs will be graded with central lab normal ranges with Gilead in-house macro. Local labs of ANC, lymphocytes, Platelet, hemoglobin, aspartate aminotransferase, alanine aminotransferase, total bilirubin, and alkaline phosphatase are included in the table summaries when central labs are not available. All other local labs are listed.

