Grade ≥ 3 diarrhea or colitis or persistent grade 2 diarrhea or colitis without clear etiology	Required Action: Withhold idelalisib.		
	Required Action: Obtain history of onset and duration of diarrhea, including description, number of stools, stool composition (e.g., watery, bloody, nocturnal), travel history, dietary changes and a medication review to identify possible diarrheogenic agents.		
	Required Action: Perform physical examination including assessment for fever, dizziness, abdominal pain/cramping, and weakness (e.g., evaluate for sepsis, bowel obstruction, dehydration).		
	Required Action: For Grade 3 colitis or diarrhea (unless clinical diagnosis is established from medical history and physical examination), perform stool culture for routine pathogens (Salmonella, Shigella, Campylobacter species, Clostridium difficile toxin, Rotavirus, Cytomegalovirus, Adenovirus), ova and parasites (Cryptosporidium parvum, Isospora belli, Enterocytozoon bieneusi, Septata intestinalis, Strongyloides, Microsporidia, Entamoeba histolytica, Cyclospora), and Giardia antigen.		
	Recommended Action: For Grade 3 colitis or diarrhea without clear etiology (eg, clostridium difficile enterocolitis), endoscopy with biopsy ^b isstrongly recommended to assess by immunohistochemistry (IHC) and PCR for CMV, Adenovirus (Optional: If ileal biopsy is performed, consider Acid Fast Bacillus staining.)		
	Recommended Action: At Grade ≤1, may resume idelalisib at lower dose level or discontinue at investigator discretion.		
	Recommended Action: Provide anti-diarrheal (eg, loperamide) and/or addition of anti-inflammatory agent (eg, sulfasalazine, budesonide).		
Hepatic Adverse Event	s (elevations in ALT, AST, or bilirubin)		
Grade ≤1 (ALT/AST≤3xULN) (Bilirubin≤1.5xULN)	Recommended Action: Maintain current dose level and schedule.		
Grade 2 (ALT/AST>3-5xULN) (Bilirubin>1.5- ≤3xULN)	Recommended Action: Monitor ALT, AST, ALP, and bilirubin at least 1x per week until all abnormalities are Grade ≤ 1; thereafter maintain current dose level.		
Grade 3 (ALT/AST>5-20xUL N) (Bilirubin>3-10xULN)	Recommended Action: Withhold idelalisib. Monitor ALT, AST, ALP, and bilirubin at least 1x per week until all abnormalities are Grade ≤1.		
	Recommended Action: If bilirubin abnormality was Grade <3, resume idelalisib at same dose level. If bilirubin abnormality was Grade >3, resume at lower dose level.		
	Required Action: Withhold idelalisib.		

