6.2. Explanation of Study Visits

The specific study procedures to be conducted for each subject enrolled in the study are presented in tabular form in Appendix 7 and are described in the sections that follow. Additional information on the study procedures is provided in the study manual.

For visits at which HRQL and healthy utility data are obtained, it is important that the subject be administered the FACT-Leu and the EQ-5D before any other procedures are performed and before any study-related information is communicated to the subject; this is necessary to avoid biasing the PRO responses provided by the subject. Once the subject has completed the FACT-Leu and the EQ-5D assessments, the remaining procedures may be performed.

At visits involving idelalisib administration and pharmacokinetic sampling in the clinic, care should be taken to perform procedures with the appropriate timing relative to idelalisib administration. The actual sample collection times of pharmacokinetic blood specimens should be recorded. If a heparinized venous catheter is placed for sample collection in order to avoid repeated needle sticks, at least 2 mL of blood should be removed and discarded prior to each sample collection in order to avoid heparin contamination of the sample.

At the visit designated as a laboratory-only visit (Visit 7), subjects will have laboratory assessments that may be performed at the investigational site or at an accredited local laboratory or clinic that is convenient for the subject/caregiver. If blood is collected at a local laboratory, samples are not to be analyzed at the local laboratory. For these visits, subjects and/or caregivers will be provided with central laboratory kits that will contain materials necessary for the collection and shipment of the laboratory samples by the local laboratory clinic to the central laboratory.

Local lab results may be requested in the event central laboratory results are not available for assessment of disease response, progression, or the evaluation of a significant event. In addition to clinical assessments of tumor status, CT or MRI imaging of the neck, chest, abdomen, and pelvis will be performed as a component of tumor assessments during the study based on the rationale provided in Section 3.2.1.

Following unblinding of the study:

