7.2.6. Liver-Related Laboratory Tests

The number and percentage of subjects will be summarized for the following liver-related laboratory tests and categories:

- AST: (a) 3 to < 5 × upper limit normal (ULN), (b) 5 to < 10 × ULN, (c) 10 to < 20 × ULN, (d) ≥ 20 × ULN
- ALT: (a) 3 to $< 5 \times$ ULN, (b) 5 to $< 10 \times$ ULN, (c) 10 to $< 20 \times$ ULN, (d) $\ge 20 \times$ ULN
- AST or ALT: (a) 3 to < 5 × ULN, (b) 5 to < 10 × ULN, (c) 10 to < 20 × ULN, (d) \geq 20 × ULN
- Total bilirubin: (a) > ULN, (b) > $1.5 \times ULN$, (c) > $2 \times ULN$
- AST or ALT > $3 \times$ ULN and total bilirubin > $1.5 \times$ ULN

- AST or ALT $> 3 \times$ ULN and total bilirubin $> 2 \times$ ULN
- Alkaline Phosphatase $> 1.5 \times ULN$

For individual laboratory tests, subjects will be counted once based on the most severe post-baseline values.

Among the subjects with elevated AST or ALT (> $3 \times ULN$), the following 2 approaches will be used for counting subjects with total bilirubin elevation/normal alkaline phosphatase ($\leq 1.5 \times ULN$):

- Subjects will be counted once when total bilirubin elevation/normal alkaline phosphatase occurred at any post-baseline visit.
- Subjects will be counted once when total bilirubin elevation/normal alkaline phosphatase occurred concurrently at the same post-baseline visit with AST or ALT elevation.

In addition, a listing of subjects meeting each category will be provided.

7.3. **Prior Therapy**

Number of prior regimens and time since the completion of last regimen collected in study GS-US-312-0116 will be summarized by treatment groups using descriptive statistics (n, mean, StD, median, Q1, Q3, minimum and maximum) based on the FAS. A partial completion date will be imputed using the following algorithm for the last regimen:

- If day and month are missing but year is available, then the imputed day and month will be 01Jan or the starting date of the last regimen, whichever is later;
- If day is missing but the month and year are available, then the imputed day will be the first day of the month, or the starting date of the last regimen, whichever is later;
- If year is missing, no imputation will be done and the completion date will be treated as missing.

Number (%) of subjects who received 1, 2, 3, ... prior regimens and the type of prior regimens that the subjects received will be summarized. The last prior regimen subjects received prior to study entry of GS-US-312-0116 will be summarized.

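### Grading local liver tests against the central laboratory's range can put values near a cut-point in the wrong CTCAE grade, in either direction

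*SAP*

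**What the plan says.** SAP 7.2.3 (Graded Laboratory Values) has hematology and chemistry results graded by program under CTCAE version 4.03. On local results it says: "Local labs will be graded with central lab normal ranges with Gilead in-house macro". It then names local ANC, lymphocytes, platelets, hemoglobin, AST, ALT, total bilirubin and ALP, which "are included in the table summaries when central labs are not available". Other local tests are only listed. Except for lipids, the normal range takes precedence where it overlaps a grade criterion, so that "all labs within normal ranges will be programmatically assigned a CTCAE grade of 0".

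Protocol 6.2 describes when local results arise: "Local lab results may be requested in the event central laboratory results are not available". The purposes given are disease response, progression "or the evaluation of a significant event". For blood drawn away from the site at the laboratory-only visit (Visit 7), "samples are not to be analyzed at the local laboratory".

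The Protocol's own laboratory analysis section (9.4.3.5) names central reference ranges only for tests that have no CTCAE scale, and does not mention local results. Neither document describes any rescaling of local values to the central scale.

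**The concern.** For ALT, AST and bilirubin a grade is a multiple of ULN, and the ULN belongs to the assay and laboratory that produced the number. Dividing one laboratory's result by another laboratory's ULN gives a ratio that is right for neither. With about 90 centers planned in the United States and Europe (SAP 1.2), a single range shared by every local laboratory should not be presumed.

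Transaminase elevation is a leading safety topic for this drug. In the Phase 1 monotherapy study, 28 of 191 subjects (15%) had Grade 3 or higher ALT/AST elevations, which were attributed to idelalisib (Protocol 1.3.5.2.1). The grades feed several outputs:

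- treatment-emergent status, which turns on a worsening of one grade from baseline (SAP 7.2.3.1);
- the worst-grade tables (7.2.3.2) and shift tables (7.2.4);
- the Grade 3/4 ALT/AST counts, resolution to Grade 1 or less, recurrence after re-challenge, and the Kaplan-Meier times to first onset and first resolution (7.2.5).

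The liver categories in SAP 7.2.6, including ALP above 1.5 x ULN, are also ULN multiples. They are exposed in the same way if the central range is applied there too. For individual tests in that section, "subjects will be counted once based on the most severe post-baseline values".

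**Working it through.** The plan states no figure on this point, so there is none to reproduce. The check is deterministic.

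**Inputs from the documents.** Protocol Table 5-2 gives the ALT/AST Grade 2 band as "ALT/AST>3-5xULN", Grade 3 as above 5 and up to 20 x ULN, and Grade 4 as above 20 x ULN. The cut-points are therefore 3, 5 and 20. For bilirubin in the same table they are 1.5, 3 and 10.

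**Assumed input.** r = local ULN / central ULN. The documents give neither ULN, so r is shown from 0.7 to 1.4.

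**Formula.** Let m be the result as a multiple of the local ULN. The SAP rule grades value / central ULN = m x r. The grade changes only if m lies between a cut-point t and t / r. If r is below 1 the result is graded too low; if r is above 1 it is graded too high.

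**Result for ALT/AST**, as bands of m (x local ULN) that change grade:

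| r | around 3 x | around 5 x | around 20 x | direction |
|---|---|---|---|---|
| 0.7 | 3.00-4.29 | 5.00-7.14 | 20.00-28.57 | down |
| 0.8 | 3.00-3.75 | 5.00-6.25 | 20.00-25.00 | down |
| 0.9 | 3.00-3.33 | 5.00-5.56 | 20.00-22.22 | down |
| 1.0 | none | none | none | none |
| 1.1 | 2.73-3.00 | 4.55-5.00 | 18.18-20.00 | up |
| 1.25 | 2.40-3.00 | 4.00-5.00 | 16.00-20.00 | up |
| 1.4 | 2.14-3.00 | 3.57-5.00 | 14.29-20.00 | up |

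For example, 5 / 0.8 = 6.25 and 5 / 1.25 = 4.00. The 5 x column decides whether a subject enters the Grade 3/4 analyses. The 3 x column decides when an episode counts as resolved to Grade 1 or less. For bilirubin at its 3 x cut-point, the band is 3.00-3.75 at r = 0.8 (3 / 0.8) and 2.40-3.00 at r = 1.25 (3 / 1.25).

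**Worked values**, with an assumed central ULN of 40 U/L:

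- Local ULN 50 (r = 1.25), ALT 210: 210 / 50 = 4.20, Grade 2. The SAP rule uses 210 / 40 = 5.25, Grade 3.
- Local ULN 32 (r = 0.8), ALT 190: 190 / 32 = 5.94, Grade 3. The SAP rule uses 190 / 40 = 4.75, Grade 2.
- Local ULN 50, ALT 400: 400 / 50 = 8.00 and 400 / 40 = 10.00, Grade 3 either way.

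**After the fix.** Where a local result is graded against its own laboratory's range, m is graded directly and the shift is zero for any r.

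**The case against.** The case on the other side is that the effect is conditional, possibly small, and easily overstated. Several stronger readings are tempting and are not supported.

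- *Local liver values are generally misgraded.* They are not. Equal ULNs change nothing, and values away from a cut-point keep their grade. At a 10% difference the band around 5 x is only 4.55-5.00 or 5.00-5.56 x local ULN.
- *The error falls mainly on acute events.* A significant event is one of three purposes in Protocol 6.2, and SAP 7.2.3 requires only that the central result is missing. Table 5-2 calls for at least weekly liver tests during Grade 2 or higher elevations while scheduled visits can be 12 weeks apart, so some clustering is plausible. No count shows it.
- *One local result decides a subject's category everywhere.* Onset and resolution in SAP 7.2.5 use the first episode. In worst-grade tables a misgraded value matters only if no other value already sets the grade.
- *The normal-range override adds a second error.* It applies where the range overlaps a grade criterion. Cut-points above 1 x ULN do not overlap a range that ends at that same ULN.
- *ALP grades are wrong too.* The documents give no CTCAE cut-points for ALP, so only the category above 1.5 x ULN can be checked. SAP 7.2.6 does not say which range it uses.

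Three further points limit the consequence. Analyses are descriptive without formal comparisons (SAP 3.5.2), adverse event severity is graded separately by investigators (SAP 7.1.2), and Listings 3.2 and 3.3 show transaminase and liver abnormalities by subject. The macro's content is also not given, so prior rescaling cannot be excluded. All of this stands as a limit on size. It does not remove the rule: as written, it misgrades any local value that falls between the cut-point multiples of the two ULNs. If the macro does rescale, the SAP should say so.

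**Conclusion.** The point holds in conditional form. SAP 7.2.3 states a grading rule that can put local ALT, AST and bilirubin results in the wrong grade, upward or downward, when the two ULNs differ and the value is near a cut-point. The same applies to the ALP category above 1.5 x ULN if the central range is used there.

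The bands in the table rest on assumed ULN ratios from 0.7 to 1.4 and on local values not being rescaled before grading. How many subjects are affected is unknown and could be none, since that depends on the ULNs and on how many local results enter the tables. The change is still worth making, because it is cheap and Grade 3/4 transaminase elevation is a central safety output.

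**What to change.** In SAP 7.2.3:

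1. Grade local ALT, AST, total bilirubin and ALP against the reporting laboratory's own normal range wherever that range was recorded, and state that the ULN categories in 7.2.6 use the same range.
2. Where no local range was recorded, keep the central range and flag the result in tables and listings.
3. Add a sensitivity table of Grade 3/4 ALT/AST using central results only.

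This changes the analysis only; no visit or treatment rule is touched. The cost is having local ranges in the database and a small amount of programming. Retrieving ranges from about 90 centers after 161 subjects have enrolled (SAP 1.3) would be a real burden, but it is not required: where ranges were not recorded, the flagged fallback and the central-only table are enough.
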